2.4.6.2 Deaths

The following summaries of deaths will be generated for the safety population.

- Number (%) of patients who died by study period (on-study, on-treatment, post-study);
- Deaths in non-randomized patients or randomized but not treated patients
- Treatment-emergent AEs leading to death (death as an outcome on the AE e-CRF page as reported by the Investigator) by primary SOC and PT showing number (%) of patients sorted by internationally agreed SOC order, with PT presented in alphabetical order within each SOC. TEAE leading to death are TEAE that led to death regardless of timing of death in relation to IMP injection (ie, death occurring in the TEAE period or during the post-treatment period).
- All deaths will be listed.

2.4.6.3 Analyses of laboratory variables

The summary statistics (including number, mean, standard deviation, median, Q1, Q3, minimum and maximum) of all laboratory variables (central laboratory values and changes from baseline) will be calculated for each visit or study assessment (baseline, each post-baseline value of the treatment period, last on-treatment and/or worst on-treatment) by treatment group, by diabetes type and in the pooled data. In addition, for some parameters of interest, mean changes from baseline with the corresponding SE could be plotted over time (at same time points) in each treatment group. This section will be organized by biological function as specified in [Section 2.1.4.3](#). For glucose, only fasting samples will be summarized.

The incidence of PCSAs (list provided in [Appendix A](#)) at any time during the TEAE period will be summarized by treatment group whatever the baseline level and/or according to the following baseline status categories:

- Normal/missing
- Abnormal according to PCSA criterion or criteria

For parameters for which no PCSA criteria are defined, similar table(s) using the normal range will be provided.

Glucose (quantitative summary and PCSA) will also be analyzed, by diabetes type and in the pooled data.

If any clinically significant signal is detected and needs further characterization, exploration of time to onset will be performed for selected PCSAs assessed during the TEAE period as described below to account for the differential exposure time in all patients.

The incidence rates of selected PCSA during TEAE period at 24 weeks of exposure will be calculated with Kaplan-Meier methodology, using the midpoint of the time interval between the first assessment with PCSA and the previous assessment. Kaplan-Meier curves will be also provided. Only the first event (PCSA) will be counted. Patients without any event will be censored at the last assessment performed during the TEAE period.

Hepatitis C antibody

The number and percentage of patients with a post-baseline seroconversion for hepatitis C test will be provided by treatment group in post-baseline period (including the TEAE and post TEAE periods) as well as in the TEAE period alone. Post-baseline seroconversion is defined for patients with a negative baseline status who had either a “positive ribonucleic acid” (RNA), a “confirmed positive antibody (Ab) with negative RNA” or a “confirmed positive antibody (Ab) with no RNA available” post-baseline status as defined in the table below. Other situations require case by case evaluation and will be described individually if relevant.

The status as regards to hepatitis C virus (HCV) for a patient will be defined as described in [Table 1](#) for all evaluations (baseline and post-baseline).

Table 1 - Definition of the patient status regarding hepatitis C virus

1st Ab		Positive						Negative					
RNA	Positive	Negative			Missing		Positive		Negative			Missing	
2nd Ab	Any result	Positive	Negative	Missing	Positive	Negative / missing	Any result	Positive	Negative / missing	Positive	Negative / missing	Positive	Negative / missing
HCV infection status	Positive RNA	Conf. positive Ab with neg. RNA	Negative	Negative RNA, conf. Ab missing	Conf. Positive Ab no RNA available	Positive Ab no RNA available	Positive RNA	Negative	Negative	Positive Ab no RNA available	Negative	Positive Ab no RNA available	Negative

The baseline evaluation will be based on tests performed during the pre-treatment period.

If no Ab test is available or with “indeterminate” as result pre-treatment or post-baseline, respectively, the RNA test (if available) will be used alone to determine the status of the patient. If no RNA is available then the hepatitis C status of the patient will be missing.

Drug-induced liver injury

The liver function tests, namely AST, ALT, ALP, and total bilirubin, are used to assess possible drug-induced liver toxicity. The proportion of patients with PCSA values or ALT increase as defined in AESI section (see [Section 2.1.4.1](#)) at any post-baseline visit by baseline status will be displayed by treatment group for each parameter.

An evaluation of drug-induced serious hepatotoxicity (eDISH) with the graph of distribution of peak values of ALT versus peak values of total bilirubin will also be presented using post-baseline values during TEAE period. Note that the ALT and total bilirubin values are presented on a logarithmic scale. The graph will be divided into 4 quadrants with a vertical line corresponding to $3 \times \text{ULN}$ for ALT and a horizontal line corresponding to $2 \times \text{ULN}$ for total bilirubin.

Listing of possible Hy’s law cases identified by treatment group (ie, patients with any elevated $\text{ALT} > 3 \times \text{ULN}$, and associated with an increase in bilirubin $> 2 \times \text{ULN}$, concomitantly or not) with ALT, AST, ALP, GGT, total bilirubin, and if available, direct and indirect bilirubin will be provided.

The incidence of liver-related TEAEs will be summarized by treatment group. The selection of PTs will be based on SMQ Hepatic disorder (see [Section 2.4.5.1](#)). Time to liver-related treatment discontinuation will be analyzed using Kaplan-Meier estimates presented by treatment group.

2.4.6.4 Analyses of vital sign variables

The summary statistics (including number, mean, standard deviation, median, Q1, Q3, minimum and maximum) of all vital signs variables (raw values and changes from baseline) will be calculated for each visit or study assessment (baseline, each post-baseline value of the treatment period, last on-treatment and/or worst on-treatment and follow-up visit) by treatment group. In addition for some parameters of interest; mean changes from baseline with the corresponding SE could be plotted over time (at same time points) in each treatment group.

The incidence of PCSAs at any time during the TEAE period will be summarized by treatment group.

If any clinically significant signal is detected and needs further characterization, exploration of time to onset will be performed for selected PCSAs assessed during the TEAE period as described below to account for the differential exposure time in all patients.

The incidence rates of selected PCSA during TEAE period at 24 weeks of exposure will be calculated with Kaplan-Meier methodology, using the midpoint of the time interval between the

first assessment with PCSA and the previous assessment. Kaplan-Meier curves will be also provided. Only the first event (PCSA) will be counted. Patients without any event will be censored at the last assessment performed during the TEAE period

2.4.6.5 Analyses of electrocardiogram variables

Not applicable.

2.4.6.6 Additional safety analysis: region North America

Additional safety analyses on selected endpoints will also be replicated in the subgroup of patients of the region North America.

2.4.7

[REDACTED]

2.4.8 Analyses of diabetes-related endpoints

The analyses of diabetes-related endpoints will be performed on the ITT and mITT populations and will be descriptive only. Summary statistics of raw values and of change from baseline of the five endpoints (see [Section 2.1.9](#)), including the mean, SD, median, Q1, Q3, minimum, and maximum, will be calculated for each visit and presented by treatment group, by diabetes type and in the pooled data .

Additional analyses of diabetes-related endpoints may also be replicated in the subgroup of patients of the region North America.

2.4.9 Analyses of ADA variables

The following summaries will be performed on the ADA population (see [Section 2.3.3](#)) taking into account all samples regardless of timing in relation to injections:

- ADA status (negative or positive) by time point and by treatment group and also according to up-titration status;
- Neutralizing status (negative or positive) by time point for positive ADA and by treatment group and also according to up-titration status;
- ADA titers using descriptive statistics (median, Q1, Q3, minimum and maximum) for positive ADA by time point and by treatment group and also according to up-titration status;
- Number (%) of patients with pre-existing ADA and number (%) of patients with treatment-emergent ADA positive response by treatment group, overall and according to up-titration status;
- Number (%) of patients with persistent/transient/indeterminate treatment-emergent ADA positive response by treatment group, overall and according to up-titration status;
- Time to onset of treatment-emergent ADA positive response using descriptive statistics by treatment group, overall and according to up-titration status.

Correlations between ADA parameters (eg, titers, status, neutralizing status) and calculated LDL-C will be also explored (eg, box plot, scatter plot):

- % change from baseline in calculated LDL-C vs neutralizing negative/positive ADA status at last value up to Week 24
- % change from baseline in calculated LDL-C vs persistent/transient/indeterminate treatment-emergent ADA positive response at last value up to Week 24
- % change from baseline in calculated LDL-C vs ADA titers at last value up to Week 24

Additional analyses of ADA parameters may also be replicated in the subgroup of patients in the region North America.

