a Weeks 4 and 32 are telephone visits only

- b Physical examination and Vital signs: Height, Weight, HR, and BP. Abnormal vital signs are to be recorded as AEs only if they are medically relevant: symptomatic, requiring corrective treatment, leading to discontinuation of IMP and/or fulfilling a seriousness criterion.
- c Injection-training prior to randomization is performed with placebo. Investigators will have the option of providing a second placebo for alirocumab for patients who require additional self-injection training. The first double-blind injection is administered at the site by the patient or a trained designated person with double-blind study treatment kit allocated by IVRS. Further training with double-blind treatment can be done at an additional unscheduled visit(s), as per patient or Investigator's judgment. If a designated person changes during the course of the study, then the person will be trained using placebo.
- d For kit dispensation: Along with kit dispensation, the treatment administration package should be given as well as the Patient diary and injection instruction manual, as needed.
- e Patients will be asked to additionally keep a log of the daily insulin dose for 7 days prior to each visit (including daily basal dose and daily prandial dose, as applicable).
- f Safety evaluation: Adverse Events (AEs), and product complaints regardless of seriousness or relationship to alirocumab treatment, will be collected from the time the patient signs the informed consent form (ICF) until the end of the study (Week 32).
- g LDL-C will be calculated using the Friedewald formula. If TG values exceed 400 mg/dL (4.52 mmol/L), then the central lab will reflexively measure (via the beta quantification method) the LDL-C rather than calculating it.

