8.4 METHOD OF ASSIGNING PATIENTS TO TREATMENT GROUP

The randomized list of treatment kit numbers will be generated centrally by Sanofi. The IMP (alirocumab 75 or 150 mg kits, or placebo kit) will be packaged in accordance with this list.

The Trial Supply Operations Manager will provide the randomized list of treatment kit numbers and the Study Biostatistician will provide the randomization scheme to the centralized treatment allocation system provider. Then, this centralized treatment allocation system provider will generate the patient randomization list according to which it will allocate the treatments to the patients.

Patients will be randomized to receive either placebo or alirocumab during the double-blind treatment period. The randomization ratio alirocumab:placebo will be 2:1. For each randomized patient, there will be several corresponding treatment kit numbers (resupply visits), which will be allocated through the centralized treatment allocation system. The randomization is stratified by diabetes type (ie, Type 1 versus Type 2).

The treatment kit numbers will be allocated using the centralized treatment allocation system on randomization visit (Day 1, Week 0), and then at Week 12 as re-supply visits, and at unscheduled visits if needed.

For patients in the alirocumab treatment arm, the treatment kit allocated at Week 12 will be based on their Week 8 LDL-C level following the up-titration rules (see [Section 6.1](#)). Regular transfer of data will be planned between the central laboratory and the centralized treatment allocation system provider in order to proceed in a blinded manner for study sites and sponsor.

Before randomizing a patient, the Investigator or designee will have to contact the centralized treatment allocation system.

A randomized patient is defined as a patient who is registered and assigned with a treatment kit number from the centralized treatment allocation system, as documented from its log file. A patient cannot be randomized more than once in the study. If a treatment is used without contacting the centralized treatment allocation system, then the patient will be considered as not randomized and withdrawn from the study.

Two types of centralized treatment allocation systems will be used, the IVRS and the IWRS depending on the choice of the site.

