- Hepatitis C antibody: at screening and Week 24; in case of ALT increase during the study, hepatitis C antibody should be determined. If Hepatitis C antibody is positive during the study, reflexive testing should be performed.
- Pregnancy testing (in women of child bearing potential only): serum pregnancy test at screening only. Urine pregnancy test at Weeks 0 and 24.
- Thyroid stimulating hormone: screening only for patients who are taking thyroid hormone replacement
- C-peptide: screening only
- PCSK9 levels will be performed only at Week 0.
- Anti-alirocumab antibodies (Week 0, Week 12, and Week 24).

Urine samplings

Urinalysis will be performed at screening and Week 24 visits. Dipstick will be performed and will assess for pH, specific gravity, and for the presence of blood, protein, glucose, ketones, nitrates, leukocyte esterase, uro-bilinogen and bilirubin. If the dipstick is abnormal then standard microscopy will be conducted. Microscopy will evaluate for the presence of red blood cells (RBC), RBC clumps, white blood cells (WBC), WBC clumps, epithelial cells (transitional, renal tubular, and squamous), casts (hyaline, epithelial, WBC, RBC, granular, fatty, cellular, broad, waxy), crystals (triple phosphate, calcium oxalate, calcium phosphate, calcium carbonate, uric acid, amorphous, ammonium biurate, bilirubin, leucine, tyrosine, cystine), bacteria, yeast- budding, yeast-hyphae, trichomonas, oval fat body, fat, mucous, and sperm.

Spot urine testing will be performed for albumin and creatinine to calculate the albumin: creatinine ratio at the screening and Week 24 visits.

Notes: Any clinically relevant abnormal laboratory value should be immediately rechecked for confirmation before making any decision for the concerned patient. It should be documented as an AE/AESI/SAE if one or more criteria in [Section 10.4](#) are met.

Decision trees for the management of certain laboratory abnormalities by Sanofi are provided in [Appendix C](#) and should be followed by Investigators.

Physical examination

A general physical examination should be performed at the time points indicated in the study schedule flowchart ([Section 1.2](#)). If a new clinically significant abnormality or worsening from baseline is detected after inclusion, then an AE should be reported and the patient should be considered for further clinical investigations and/or specialist consultation, as per the Investigator's medical judgment.

Blood pressure/heart rate

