2.1.10 Anti-alirocumab antibodies

Descriptive statistics on ADA (status, neutralizing status and titer) collected at Week 0, Week 12, and Week 24 will be provided.

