2.4.4.1 Titration

The number and percentage of patients with an up-titration in the alirocumab group will be described. Patients with an up-titration are defined as up-titrated patients according to IVRS/IWRS Week 12 transaction with at least 1 injection of alirocumab 150 mg afterwards.

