- For exploratory purpose, all TEAEs will be described by SOC, HLTG, HLT and PT according to up-titration status, ie, according to whether the patients remained on the 75 mg dose or whether they were up-titrated to 150 mg. These analyses will be exploratory and descriptive (no formal comparison per dose) as it is expected that there could be inherent differences in the baseline characteristics between those patients titrating to 150 mg and those remaining on 75 mg. In order to reduce the bias of this analysis, the period before the up-titration time point (planned at Week 12) will be analyzed separately since only the dose 75 mg is proposed for this time period and consequently the early events occurring before Week 12 can only be attributed to this dose. Therefore the descriptive analysis per dose will include any safety events occurring from the first injection post Week 12 IVRS/IWRS transaction to the end of the TEAE period. Baseline characteristics of patients receiving each dose will be summarized.

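### The antibody summaries by up-titration status in SAP 2.4.9 count responses that arose on 75 mg in the up-titrated column, because they lack the post-Week 12 cut that SAP 2.4.6 applies to adverse events

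*SAP*

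**What the plan says.** **Sampling.** SAP 2.1.10 states: "Descriptive statistics on ADA (status, neutralizing status and titer) collected at Week 0, Week 12, and Week 24 will be provided". Protocol section 10 lists the same three weeks. The only contact after Week 24 is by phone: "Weeks 4 and 32 are telephone visits only" (Protocol 1.2).

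**Dosing.** Every alirocumab patient starts on 75 mg. For these patients, "the treatment kit allocated at Week 12 will be based on their Week 8 LDL-C level" (Protocol 8.4), so 150 mg cannot start before the Week 12 visit. Protocol 8.1.2 and section 10 place blood sampling before the injection on a visit day.

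**The split.** SAP 2.4.4.1 defines an up-titrated patient by the Week 12 IVRS/IWRS transaction, "with at least 1 injection of alirocumab 150 mg afterwards". This is one flag per patient, not the dose in use when a sample was taken.

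**The antibody tables.** SAP 2.4.9 takes all samples, with no cut by injection date. Status, neutralizing status and titer are shown by time point and by up-titration status. Three further summaries are split by up-titration status but not by time point: pre-existing and treatment-emergent response, time to onset, and "Number (%) of patients with persistent/transient/indeterminate treatment-emergent ADA positive response by treatment group, overall and according to up-titration status".

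**The adverse-event table.** SAP 2.4.6 also describes adverse events by up-titration status. It reasons that "the early events occurring before Week 12 can only be attributed to this dose", meaning 75 mg. It therefore analyses the earlier period separately and counts only events from the first injection after the Week 12 transaction, expressly to reduce bias.

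**The concern.** The flag is fixed at or after Week 12, but the three summaries reach back to the first injection. A patient who turns antibody-positive on 75 mg and is later up-titrated is counted in the up-titrated column, and nothing in those tables separates that patient from one who turned positive after moving to 150 mg.

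The path could also be selective. Up-titration depends on Week 8 LDL-C, and SAP 2.4.9 itself plans to explore how antibodies relate to the LDL-C change. If early antibodies blunted the LDL-C response, antibody-positive patients would be up-titrated more often, and a response that preceded the higher dose would be tabulated beside it. The documents do not say that this happens, but the table could not reveal it.

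The columns also differ in their entry conditions. Up-titrated patients must have had an injection after Week 12. SAP 2.4.9 states no matching condition for the others, so early dropouts with fewer samples may fall there.

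Evaluating antibody development is a listed objective (SAP 1.2.3). At stake is a descriptive table that readers may take as information about the higher dose.

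**Working it through.** The plan gives no figure to reproduce. The check is a timeline, an enumeration of result patterns, and an illustration under stated assumptions.

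**1. Timeline for an up-titrated patient** (visit days from Protocol 1.2)

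- Week 12 sample: Day 85 ± 3, so Day 82 to 88, before the first 150 mg injection.
- Week 24 sample: Day 169 ± 3, so Day 166 to 172.
- Gap: 166 − 88 = 78 days to 172 − 82 = 90 days.
- 150 mg injections before the Week 24 sample: Weeks 12, 14, 16, 18, 20 and 22, so up to 6.
- The Week 12 analysis window in SAP 2.5.4, which covers antibodies, closes no later than the first injection from the up-titration kit.

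One scheduled antibody sample therefore follows the first 150 mg injection.

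**2. Scheduled result patterns, antibody-negative at baseline**

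| Week 12 | Week 24 | Onset | Scheduled samples after first positive |
|---|---|---|---|
| + | + | on 75 mg | 1 |
| + | − | on 75 mg | 1 |
| − | + | after Week 12 | 0 |
| − | − | none | not applicable |

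On the schedule alone, every response in the up-titrated column that has any follow-up after its first positive began on 75 mg.

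**3. Unscheduled samples**

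- Protocol 10.3.4 asks for a visit with end-of-treatment assessments, which include antibodies (Protocol 10.1.2.4), within 5 days of permanent discontinuation if possible. The original schedule then resumes. For an up-titrated patient who stops on Day 99, 113, 127 or 141, the extra sample falls by Day 104, 118, 132 or 146. The time to Day 169 is then 65, 51, 37 or 23 days.
- Protocol 10.6.2.1 adds an antibody sample for allergic events with cutaneous involvement.

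Either route can give a second sample after 150 mg.

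**4. Illustrative size**

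Assume the same risk p of a new positive in each 12-week period on 75 mg, with p from 2% to 10%. Let RR be the risk ratio on 150 mg after Week 12. No document gives p or RR.

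Share of new positives in the up-titrated column that predate 150 mg, with RR = 1:

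p / [p + (1 − p)p] = 1 / (2 − p)

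- p = 0.02: 1/1.98 = 0.51
- p = 0.05: 1/1.95 = 0.51
- p = 0.10: 1/1.90 = 0.53

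Ratio of whole-study incidence, up-titrated to not up-titrated:

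[1 + RR(1 − p)] / (2 − p)

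- RR = 2: 1.49, 1.49 and 1.47 for p = 0.02, 0.05 and 0.10.
- RR = 3: 1.99, 1.97 and 1.95.

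If instead 150 mg has no effect, but patients later up-titrated had k times the Week 12 positivity, the ratio is (k + 1 − kp) / (2 − p):

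- k = 1.5: 1.25, 1.24 and 1.24.
- k = 2: 1.49, 1.49 and 1.47.

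Under these assumptions, the whole-study incidence hardly distinguishes a doubling of risk on 150 mg from a twofold imbalance already present at Week 12.

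**The case against.** **A reader might infer that a response arising on 150 mg can never be classed as persistent or transient.** The documents do not support this. Scheduled sampling ends at Week 24, but the unscheduled samples in step 3 can supply a second time point, and SAP 2.4.9 admits all samples. Whether 23 to 65 days would be enough for persistent cannot be judged, because the text available does not define the classes. These samples are triggered by stopping treatment or by an allergic event, so they qualify the statement without repairing the table. Nor is a Week 24 first-positive misreported if it is placed in the indeterminate class.

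**A reader might call the column a 150 mg group and these tables the only antibody comparison between doses.** Neither holds. The column is labelled by up-titration status, and SAP 2.4.9 does not itself attribute a response to a dose. Status, neutralizing status and titer are shown by time point, so a Week 12 imbalance would be visible there. That limits the harm but leaves the three whole-study summaries unchanged.

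**A reader might treat the ratios in step 4 as a diluted dose effect.** Up-titration is not randomised, and SAP 2.4.6 expects inherent differences between the groups and plans no formal comparison. The SAP plans counts and percentages, not ratios. The cut corrects timing; it does not create an unbiased dose contrast.

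**The tables are descriptive.** This stands: no test, alpha or decision depends on them.

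**Conclusion.** The point holds for the three summaries not shown by time point. The scheduled Week 12 sample reflects 75 mg only, yet responses found there are counted in the up-titrated column, while SAP 2.4.6 removes the same problem from the parallel adverse-event analysis. The available text gives no reason for the difference.

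On scheduled samples, a response first seen after up-titration has no follow-up. The persistent and transient entries in the up-titrated column therefore reflect onset on 75 mg, except for patients with unscheduled samples.

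The timing argument rests on the documents alone. The size does not: the share of about one half (51% to 53%) assumes equal risk in both periods, no dose effect, and new positives only, ignoring pre-existing antibodies. This is a cheap improvement to a descriptive display, with no bearing on the primary or key secondary results or on type I error.

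**What to change.** In SAP 2.4.9, adopt the cut already used in SAP 2.4.6:

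1. Report treatment-emergent responses first detected up to the Week 12 sample separately, as onset on 75 mg.
2. Give incidence by up-titration status only for responses first detected after the first injection following the Week 12 IVRS/IWRS transaction, among patients who had such an injection. State how pre-existing antibodies and a missing Week 12 sample are handled.
3. Keep response class and time to onset, but show them by period of first detection. Add a note that patients first positive at Week 24 have no scheduled follow-up.
4. List individually the patients with unscheduled later samples.

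The cost is SAP wording and table shells; no new samples are needed. The downside is smaller counts in the table by up-titration status. The comparison remains descriptive and non-randomised.
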